This IVACFLU-A/H5N1 Phase 2/3 is a double-blind, randomized, placebo-controlled trial to test the safety and immunogenicity of two doses given 21 days apart of the IVAC A/H5N1 vaccine. Subjects will be male and female healthy adults from 18 through 60 years of age. In the Phase 2 study which was a dose-selection study and was conducted at one site (Khanh Hoa), 300 male and female healthy adult subjects from 18 through 60 years of age were randomized to receive 15 mcg of vaccine (n=100), 30 mcg of vaccine (n=100), or saline placebo (n=100). The details of the interim analysis plan for the Phase 2 study had been prepared separately.

The Phase 3 is a confirmatory study that will expand the safety and immunogenicity in a larger number of subjects to meet product registration in Vietnam. In Phase 3, subjects will be randomized to receive the selected vaccine 15 mcg dose (n=500) or saline placebo (n=100) under double blind. Safety will be assessed in all subjects and immunogenicity will be measured by Hemagglutination Inhibition test (HAI) in a subset of approximately 270 subjects receiving the IVACFLU-A/H5N1 (n=225 vaccinees) and placebo (N=45) from all subjects enrolled at one of 2 study sites (Hai Phong) in Phase 3.

This final analysis plan will mainly focus on the analyses of Phase 3 cohort with additional analyses combining subjects from both phases if needed.

I. OBJECTIVES

The study objectives and endpoints for Phase 3 as described in the protocol are as follows:

Primary Objective	Endpoint
Safety: To evaluate the safety and tolerability of two injections given 21 days apart of A/H5N1 vaccine at the dose level of 15 mcg.	
The safety profile of IVACFLU-A/H5N1 will be evaluated by the proportion of subjects experiencing AEs, related or not related, of the following five categories for all subjects and by age group (18-40 years of age and 41-60 years age):
 
• Number and percentage of subjects with solicited local and systemic adverse events within 30 minutes after each vaccination.• Number and percentages of subjects with solicited local adverse events (redness, swelling, pain, induration, and tenderness) over a 7-day period (Days 1-7; Days 22-28) post each vaccination.• Number and percentages of subjects with solicited systemic/general adverse events (fever, fatigue/malaise, muscle aches (generalized), joint aches, chills, nausea, vomiting, and headache) over a 7-day period (Days 1-7; Days 22-28) post each vaccination.

	
 Number and percentages of subjects with unsolicited adverse events for 21 days post each vaccination. All serious adverse events (SAEs) occurring over the entire study period. (Days 1-91).
Immunogenicity: To evaluate the immunogenicity of the A/H5N1 influenza vaccine as determined by serum HAI titer $\geq 1:40$ at Day 43 in a sample of approximately 270 subjects receiving the IVACFLUA/H5N1 (vaccinees) and placebo.	
Primary: Percentage of subjects achieving an HAI titer $\geq 1:40$ after the second vaccination on Day 43.
 
Secondary:
 
 The percentage of subjects achieving a seroresponse (at least a four-fold increase in post-vaccination titer) on Day 43 as determined by HAI. Geometric Mean Titer (GMT) of Day 43 as determined by HAI. Geometric Mean Titer Ratio (GMTR) of Day 43/Day 1 as determined by HAI.

II. ANALYSIS POPULATIONS

The need for different analysis populations depends on how well the protocol is followed by study personnel and participants as well as the objectives of specific analyses. The final statistical report will include an accounting of all persons screened, including the number enrolled, the number followed during the study, and other key study status indicators. The reason for excluding any data from any analysis population will be documented.

A. Enrolled Population

All screened subjects who provide informed consent, regardless of the subject's randomization and treatment status in the trial.

B. Full Analysis (FA) Population

All subjects in the enrolled population who were randomized, received a study vaccination. This population will serve as the primary analysis population for all safety objectives. The immunogenicity analysis based on this population will serve as the supportive results for all immunogenicity objectives. Subjects who withdraw or are terminated from the study will be included in the FA data set until the time of withdrawal or termination. Subjects will be analyzed as received; that is, allocation errors, if any, are taken into account.

C. Per Protocol (PP) Population

All subjects in the Full Analysis population who have valid baseline (Day 1)¹ and a post-vaccination immunogenicity measure with no major protocol violations that are determined to potentially interfere

¹ The protocol does not state this requirement.

with the immunogenicity assessment of the study vaccine (e.g., missed the 2nd vaccination). This population will serve as the primary analysis population for all immunogenicity objectives.²

The criteria for exclusion of subjects from the Full Analysis Population and Per Protocol Population will be established by the study statistician and the study medical officer before breaking the blind and will be based on the blinded review of protocol violations.

III. MISSING DATA

In the event that missing visit dates or study contact dates are needed to be imputed for couples of study forms, the following rules will be applied:

- The month and year are known, but the date was missing, the 15th was used for any calculations of relative time (e.g., UNMAY2016 will become 15MAY2016).

For missing safety related data, the following rules will be applied:

- For solicited AEs, if the severity for all 7 days are missing or the diary card was not completed or was marked as ‘unknown’ then the aggregated value will be set to missing and the subject will be excluded from the analysis. If the intensities are missing for only some of the days then the missing intensities will be evaluated as the maximum of the previous and next non-missing value for calculation of the aggregated value. For example if fever intensity is recorded as 1, (blank field), 2, 0, 0, for day 0 to day 4, then the missing day 2 intensity is imputed to be 2. Severity is missing for any AE then it will be considered as AE of maximum severity (Grade 3) “Severe” unless it’s captured as SAE. For SAE missing severity will be considered as maximum severity (Grade 4) “Life Threatening”
- If “Relationship” is missing then it will be considered as “Related” to vaccine administered i.e. study vaccine/ placebo.
- If for Start date - day of event / condition is missing for any adverse event then it will be imputed as the date of last dose of study vaccine / placebo.
- If for Start date - day and month of any adverse event is missing then it will be imputed as the date of first dose of study vaccine / placebo.
- If Stop date of any adverse event is missing then it will be treated as missing.

All immunogenicity assays reported below the limit of quantification (LLOQ, e.g. <1:10) will be assigned a value by the study lab. No missing data will be imputed.

² This definition is similar to the criteria: 1) the completion of a certain pre-specified minimal exposure to the treatment regimen; 2) the availability of measurements of the primary variable(s); 3) the absence of any major protocol violations including the violation of entry criteria; that given by ICH guideline E9: statistical principles for clinical trials: International Conference on Harmonisation of Technical Requirements for Registration of Pharmaceuticals for Human Use; 1998. Available from: <http://www.ich.org/products/guidelines/efficacy/article/efficacy-guidelines.html>.

IV. UNBLIDING STUDY CODE FOR FINAL DATA ANALYSES

Before unblinding the study data, FHI360 statisticians will provide blinded data to the study statistician and the study medical officer to establish the criteria for exclusion of subjects from the Full Analysis Population and Per Protocol Population, and to review protocol violations. The final data analysis will initially be prepared with blinded study product group. After all analysis programs and output tables for the final analyses are verified, all analysis programs will be re-ran with the unblinded study product code given by the study randomisation statistician. In addition, the FHI360 randomisation statistician will verify with IVAC that no errors were made in study product assignment and dispensing of vaccines.

V. MULTIPLICITY CONSIDERATION

In general, since the purpose of the Phase 2 assessment is to select the dose for the Phase 3 component and the final confirmatory analysis will be solely based on the data generated for the Phase 3 component, there is no need to make an adjustment to the Type I error rate between the Phase 2 and Phase 3 components of the study.

Specifically, the analysis of immunogenicity data has a single primary endpoint and it maintains the experiment-wise Type I error rate at 2-sided of 0.05. No multiplicity adjustment to the error rate, alpha, will be made for secondary immunogenicity endpoints.

In addition, no formal hypothesis testing will be conducted for safety data analyses, therefore, no multiplicity adjustment will be performed.

VI. DESCRIPTIVE ANALYSIS

A. Study Participant Disposition

A flowchart or table showing the number screened, enrolled, randomized, vaccinated, withdrawn and its reasons, and numbers in the Full Analysis and Per Protocol Populations with protocol deviations reported on the Protocol Deviation/Violation (PDV) CRF will be produced.

B. Descriptive Statistics

Descriptive statistics will be presented in summary tables by each group, each time visit and overall. Categorical variables will be summarized by frequencies and percentages. Continuous variables will be summarized by means, standard deviations, medians, interquartile ranges, minima and maxima.

C. Baseline Data

Following information on enrollment will be summarized by study group for FA Population; baseline demographics, medical history, vital signs, pregnancy test and general physical examination. Baseline measures are those obtained closest to but preceding randomization and vaccine #1. No inferential statistics (e.g. p-values, confidence intervals) will be computed comparing treatment groups on baseline variables.

D. Laboratory Data

The immunogenicity measures will be expressed by Hemagglutination Inhibition (HAI) titers and also expressed as geometric mean titer (GMT) of the antibody response. Because titers are often approximately lognormally distributed, they are customarily analyzed on a logarithmic (log) scale; a difference in arithmetic means on a log scale becomes a ratio of geometric means when the results of analysis are converted back to the original data scale.³

It is possible that samples fall below the cut-off or LLQ of some antigens. Values below the cut-off of the assay will be given an arbitrary value of half the LLQ for the purpose of the calculation. Similarly, for lab value above Method detection limit (MDL) an arbitrary value of 2-fold the MDL will be given for the purpose of the calculation. The final details about the cut-off values will be provided by the study lab.

For each group and at each time-point (Day 1 and Day 43) that a blood-sample result was available following descriptive analyses were performed:

- Frequencies and proportions of available specimens, valid immune responses and measurements below/above certain cut-off will be tabulated.
- GMTs and their 95% confidence intervals (CIs) will be calculated by taking the anti-log of the mean of the log concentration or titer transformations.
- Distributions of antibody titers (log scale) will be displayed using reverse cumulative distribution curves.
- The reasons for excluding from the immunogenicity analysis will be listed.

VII. ANALYSIS OF IMMUNOGENICITY OBJECTIVES

Objective: To evaluate the immunogenicity of the A/H5N1 influenza vaccine as determined by serum HAI titer $\geq 1:40$ at Day 43 in a sample of approximately 270 subjects receiving the IVACFLUA/H5N1 (vaccinees) and placebo.

Analysis Population: All immunogenicity endpoint analyses and summaries will be performed on a per-protocol basis for all subjects and by age group (18-40 years of age and 41-60 years age). Supportive analysis will also be conducted on participants in the FA population who received at least one dose of study vaccines if the difference in the number of subjects between the FA and PP populations exceeds 5%.

Study Endpoints

Primary:

- Percentage of subjects achieving an HAI titer $\geq 1:40$ after the second vaccination on Day 43

Secondary:

- The percentage of subjects achieving a seroresponse (at least a four-fold increase in post-vaccination titer) on Day 43 as determined by HAI
- Geometric Mean Titer (GMT) of Day 43 as determined by HAI.

³ Horne AD, Lachenbruch PA, Getson PR, and Hsu HS Analysis of Studies to Evaluate Immune Response to Combination Vaccines. Clinical Infectious Diseases 2001; 33(Suppl 4):S306-11

- Geometric Mean Titer Ratio (GMTR) of Day 43/Day 1 as determined by HAI.

Analysis Methods

There are two types of immunogenicity measurements, percentages of subjects with immune response and Geometric Mean Titers (GMT), that will be used to evaluate this study objective.

Percentages of subjects with immune response:

- Percentage of subjects achieving an HAI titer $\geq 1:40$ ⁴ on Day 43.
- Percentage of subjects demonstrating an HAI seroresponse of at least a four-fold increase in postvaccination titer on Day 43.

For each percentage of subjects with the defined immune responses, the percentage and its corresponding 2-sided exact (Clopper-Pearson) binomial 95% confidence interval (95% CI) around the percentage will be computed for each treatment group and by age group.

Geometric Mean Titers (GMTs):

- Geometric Mean Titer (GMT) of Day 43 as determined by HAI
- Geometric Mean Fold Rise (GMFR): Geometric Mean of Titer Ratio of Day 43/Day 1 as determined by HAI.

GMT along with the corresponding two-sided 95% CIs, by exponentiating the corresponding log-transformed means and their 95% CIs, will be summarized by treatment group on Day 1 and Day 43. The same approach will be used to summarize GMFR of Day 43/Day 1 separately by treatment group and age group.

Furthermore, the analyses will be repeated by combining the immunogenicity measures of the selected dose group and the placebo group from both Phases 2 and 3 cohorts if needed. No comparisons will be made between the IVACFLU-A/H5N1 dose group and the placebo group.

VIII. ANALYSIS OF SAFETY OBJECTIVES

Objective: To evaluate the safety and tolerability of two injections given 21 days apart of A/H5N1 vaccine.

Analysis Population: The Full Analysis Population will be used for the safety objective analysis.

⁴ Note that this endpoint is expected to be equivalent to another commonly used endpoint of seroconversion as defined as a post-vaccination titer $\geq 1:40$ if baseline titer $< 1:10$ OR significant increase in antibody titer post vaccination (at least a four-fold increase from baseline titer) if baseline titer is $\geq 1:10$, since all subjects are expected to have baseline titer of $< 1:10$. If at least one subject has baseline titer $\geq 1:10$, an additional endpoint of seroconversion as defined above will also be analyzed

Endpoints: The safety profile of IVACFLU-A/H5N1 will be evaluated by the number and the proportion of subjects experiencing AEs, related or not related, of the following categories for all subjects and by age group (18-40 years of age and 41-60 years age):

- **Immediate reactions** (solicited local and systemic adverse events), occurring in the first 30 minutes post vaccination on Day 1 and Day 22, as observed by study staff. The reaction will include
 - Local signs/symptoms: redness, swelling, hardness, pain, or tenderness of the injected site of upper arms;
 - Systemic signs/symptoms: headache, fever, fatigue/malaise, muscle aches, joint aches, nausea, vomiting, and chills.
- **Solicited adverse local reactions** occur over a 7-day period (Days 1-7; Days 22-28) post each vaccination, identified or observed by study staff during home visits and/or reported by parent at any time through Day 7. Specifically, the following local signs and symptoms at site of injection will be assessed and documented as solicited adverse reactions:
 - Redness
 - Swelling
 - Induration
 - Pain
 - Tenderness
- **Solicited adverse systemic reactions** occur over a 7-day period (Days 1-7; Days 22-28) post each vaccination, identified or observed by study staff during home visits and/or reported by parent at any time through Day 7. Specifically, the following systemic reactions will be assessed and documented as solicited adverse reactions:
 - Fever/body temperature (and body location of measurement)
 - Fatigue/malaise
 - Generalized muscle aches
 - Joint aches/pains
 - Chills
 - Nausea
 - Vomiting
 - Headache

If a solicited sign or symptom has started during the 7 days post vaccination and continues beyond the 7 days, it will continue to be reported as a reactogenicity symptom. Any solicited sign or symptom starting after 7 days post vaccination will be recorded as an “unsolicited AE”. Adverse reactions will be graded (i.e., Grade 1 to 4).

- **Unsolicited adverse events** are any AEs that occur any time after the vaccine/placebo is given (temporally related to study product), whether or not deemed “related” to the product, and are not solicited (specifically asked of the subject). Unsolicited AEs can be observed by study staff while the subject is at a clinic for a study visit or reported by the subject at any time, and subcategorized as those deemed related to vaccination or not by a study clinician.

- **Serious adverse events (SAEs)** occur from vaccination through 3 months (Days 1-91) post-vaccination, identified or observed by study staff and/or reported by parent at any time. SAEs will be graded for severity and subcategorized as those deemed related to vaccination or not by a study clinician. All SAEs will be listed.
- **Targeted physical examination and vitals data** will be summarized for post-vaccination measurements, separately by visit or time point of observation.

Analysis Methods

In general, adverse events (AEs) will be summarized by MedDRA System/Organ Class (SOC) and adverse event type (MedDRA Preferred Term), using the MedDRA dictionary in production at FHI 360 at the time the database is developed. As needed, this AE summary will be repeated for (a) AEs considered related to study product and (b) serious AEs (SAEs).

Unsolicited AE summaries will report the number of persons with at least one episode of the given AE type/SOC, as well as the number of episodes. In calculating percentages, each person will contribute only once to a given AE type/SOC no matter the number of episodes experienced. Percentages of subjects experiencing each reaction or event, or at least one reaction or event, will be calculated along with two-sided exact (Clopper-Pearson) binomial 95% CIs.

For the solicited local and systemic/general adverse events, Fisher's exact test for two proportions or the Cochran-Mantel-Haenszel test⁵ for severity grade categories at 2-sided 0.05 alpha will be used to compare the treatment groups. No formal hypothesis testing with multiplicity adjustment will be performed. Furthermore, no statistical testing will be performed for unsolicited AEs including SAEs.

In addition, subject listings of adverse events will include details such as the following: MedDRA codes, study day of onset, seriousness, duration, action/treatment, outcome, severity, relatedness, and current status. Concomitant medications will also be coded and listed.

Furthermore, additional analyses will be repeated by combining safety outcomes of the selected dose group and placebo group from both Phases 2 and 3 cohorts if needed.

⁵ The Cochran-Mantel-Haenszel test is better method for comparing severity grade categories than the Chi-squared test as proposed in the study protocol

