4.4 Research Duration

The total time for conduct of the research is approximately 14-16 months. Recruitment and screening is expected to take approximately 5 months (1-1.5 months for the initial cohort and 4-5 months for the remaining cohort). Once enrolled, each subject will be in the study for approximately 3 months (6 weeks of active visits, then passive participation until a phone call at Day 91).

There will be approximately a 8- to 10-month break for an early evaluation of the immunogenicity and safety of the Phase 2 cohort of 300 subjects up to Day 43 before continuing with screening and enrollment of the Phase 3 study cohort.

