6.7 Unauthorized Products

The following products are not authorized to be used during the study:

1. Any concomitant medicine or biologic specifically prescribed for the treatment of a condition which is an exclusion criterion for participation in the trial.
2. All non-study vaccines or biologics (including blood products).

Other concomitant medications will be reviewed on a case-by-case basis if the study staff are unclear.

Subjects will be requested not to take analgesic or antipyretic drugs *in a preventive way* (before or soon after injection), as such medications might change the reactogenicity profiles of study vaccine and placebo.

During the trial, if a situation arises where there is an adverse reaction or AE requiring treatment and prescription of unauthorized products or products not stipulated by the protocol, then such products may be prescribed. However, IVAC must be informed of such an occurrence within 48 hours. Information on the products (trade name, dosing or change in dosing, indications, start date, and termination date) must be recorded in the CRF.

7 Study Schedule; Description of Visits

The total expected duration of the study:

First subject enrolled in study	Day 1 of first subject
The last subject enrolled in study	For Phase 2: Day 1 of last subject is estimated 2-4 weeks from Day 1 of first subject; Phase 3: Day 1 of last subject is estimated approximately 18 months after the Day 1 of first subject from Phase 2.
The last subject completes the trial	Day 91 of last subject
Lock database	8 weeks after Day 91 of last subject for each Phase
Clinical trial report	8-10 months after Day 91 of last subject for Phase 3

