9.5.2 Data and Safety Monitoring Board

A DSMB comprised of independent vaccine and infectious diseases experts and a biostatistician will (1) review the initial cohort of trial participants and advise on continuing with vaccinations for the rest of the study and (2) periodically review cumulative data. To allow for accurate assessment, the DSMB will

review reports that have been unblinded to the study code. Investigators and other persons associated with the conduct trial will remain blinded.

Initial Cohort Review:

After 300 subjects receive both vaccinations, further enrollment in the study will pause for approximately 6 months while the immunogenicity and safety data are compiled by the Data Management CRO and reviewed by the DSMB. Study enrollment will proceed if the DSMB advises continuation of the trial and the Vietnam Ministry of Health concurs.

Periodic Review:

The DSMB will conduct periodic review of (but will not be limited to): demographic information on study; interim/cumulative data for evidence of study-related AEs; discontinuations of study vaccinations; data quality, completeness, and timeliness; factors that might affect the study outcome or compromise the confidentiality of the trial data (such as treatment and endpoint unblinding); and, factors external to the study such as scientific or therapeutic developments that may impact participant safety or the ethics of the study.

The DSMB reviews will be summarized and contain recommendations to the study sponsor concerning whether or not there are safety concerns, if the study should continue without change or modified, or if it should be terminated. Decisions regarding permanent discontinuation of study product in individuals will be made by the PSRT based on careful review of all relevant data and by consulting with the DSMB, if necessary. Although it is not likely to happen, if the protocol team has serious safety concerns with the study and concludes the study product should no longer be administered and accrual into the protocol should stop, the team should request a review of the data by the DSMB. If, at any time, a decision is made to discontinue the study product for all participants, IVAC will notify the MOH and the site investigators of record will notify the responsible IRBs/IECs expeditiously.

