28.2 Planned Interim Analysis

The interim assessment will be performed when the safety and immunogenicity data through Day 43 visit is available for 300 subjects in the Phase 2 component. The purpose of this interim assessment is determined a dose to be studied in the Phase 3 component.

The interim assessment will be performed by a third party who is not involved in the conduct of the study. The unblinded results summarized by treatment group and the final decision will be submitted to the Vietnamese MOH for their review prior to the resumption of the enrollment. No individual listing will be generated. This interim assessment will not otherwise alter the course of the trial and blinded status of the study.

Since the purpose of this interim assessment is to select the dose for the Phase 3 component and the final confirmatory analysis will be solely based on the data generated for the Phase 3 component only, there is no need to make an adjustment to the Type I error rate.

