Although full evaluation of the safety will continue through Day 91, this interim analysis will evaluate the complete safety and immunogenicity data collected through Day 43 of Phase 2 cohort to determine whether to proceed to Phase 3 and what dose to select. Vaccination of subjects in Phase 3 component will not begin until the DSMB has reviewed safety and immunogenicity data through Day 43 of phase 2 for all participants and concurs with the progression. The conduct of Phase 3 will be dependent on a post dose two HAI titer of $\geq 1:40$ in 60% or more vaccine recipients in at least one of the two vaccine groups in Phase 2 cohort.

I. OBJECTIVES

The study objectives and endpoints for Phase 2 as described in the protocol are as follows:

Primary Objective	Endpoint
Safety: To evaluate the safety and tolerability of two injections given 21 days apart of A/H5N1 vaccine at two dose levels (15 and 30 mcg).	
The safety profile of IVACFLU-A/H5N1 will be evaluated by the proportion of subjects experiencing AEs, related or not related, of the following five categories for all subjects and by age group (18-40 years of age and 41-60 years age):
 
Number and percentage of subjects with solicited local and systemic adverse events within 30 minutes after each vaccination.Number and percentages of subjects with solicited local adverse events (redness, swelling, pain, induration, and tenderness) over a 7-day period (Days 1-7; Days 22-28) post each vaccination.Number and percentages of subjects with solicited systemic/general adverse events (fever, fatigue/malaise, muscle aches (generalized), joint aches, chills, nausea, vomiting, and headache) over a 7-day period (Days 1-7; Days 22-28) post each vaccination.

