
Immunogenicity: To evaluate the immunogenicity of two different doses (15 mcg and 30 mcg) of A/H5N1.
	
 Number and percentages of subjects with unsolicited adverse events for 21 days post each vaccination. All serious adverse events (SAEs) occurring over the entire study period. (Days 1-91). 
Primary: Percentage of subjects achieving an HAI titer $\geq 1:40$ after the second vaccination on Day 43
 
Secondary:
 
 Percentage of subjects with a serum HAI titer $\geq 1:40$ at Day 22. Percentage of subjects demonstrating an HAI seroresponse of at least a four-fold increase in postvaccination titer on Day 22 and Day 43. Percentage of subjects with at least a four-fold rise in titer at Day 22 and Day 43, as determined by microneutralization (MN). Geometric Mean Titer (GMT) of Day 22 and Day 43 as determined by the HAI and MN tests. Geometric Mean Titer Ratio (GMTR) of Day 22/Day 1 and Day 43/Day 1 as determined by the HAI and MN tests.
--	---

II. ANALYSIS POPULATIONS

The need for different analysis populations depends on how well the protocol is followed by study personnel and participants as well as the objectives of specific analyses. The final statistical report will include an accounting of all persons screened, including the number enrolled, the number followed during the study, and other key study status indicators. The reason for excluding any data from any analysis population will be documented.

A. Enrolled Population

All screened subjects who provide informed consent, regardless of the subject's randomization and treatment status in the trial.

B. Full Analysis (FA) Population

All subjects in the enrolled population who were randomized, received a study vaccination. This population will serve as the primary analysis population for all safety objectives. The analysis based on this population may serve as the supportive results for all immunogenicity objectives. Subjects who withdraw or are terminated from the study will be included in the FA data set until the time of withdrawal or termination. Subjects will be analyzed as received; that is, allocation errors, if any, are taken into account.

C. Per Protocol (PP) Population

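### The by-arm safety report that opens Phase 3 stops at Day 43 and so covers the Days 1-91 SAE endpoint only in part, although every Day 91 call fits inside the planned pause

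*SAP*

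**What the plan says.** - **Data cut.** The interim SAP, Preface, states that "this interim analysis will evaluate the complete safety and immunogenicity data collected through Day 43 of Phase 2 cohort", and that Phase 3 vaccination "will not begin until the DSMB has reviewed safety and immunogenicity data through Day 43 of phase 2 for all participants". Protocol 28.2 sets the trigger: "The interim assessment will be performed when the safety and immunogenicity data through Day 43 visit is available for 300 subjects".
- **Endpoints.** Interim SAP section I lists five Phase 2 safety categories. One is "Number and percentages of subjects with unsolicited adverse events for 21 days post each vaccination", a window that closes at about Day 43. Another is "All serious adverse events (SAEs) occurring over the entire study period. (Days 1-91", which runs well past the cut. Section VIII repeats the Days 1-91 window for SAEs.
- **Pause.** Protocol 9.5.2 says that, once 300 subjects have had both injections, "further enrollment in the study will pause for approximately 6 months while the immunogenicity and safety data are compiled". Protocol 4.4 gives another length: "There will be approximately a 8- to 10-month break for an early evaluation".
- **Lock.** The schedule table that opens protocol section 7 puts database lock at "8 weeks after Day 91 of last subject for each Phase".
- **Follow-up after Day 43.** Protocol 4.4 describes it as passive until a phone call at Day 91. Section 7.3.10 makes that call the point at which new SAEs are asked about.

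Both documents state openly that full safety evaluation continues to Day 91. Neither says how SAEs from Day 44 onward enter the report that the DSMB uses to advise on Phase 3.

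**The concern.** The interim report supports two decisions: which dose goes forward, and whether to expose the Phase 3 cohort (1,000 vaccinees in the protocol, 500 in the final SAP). One of its pre-specified safety endpoints is only partly observed at the data cut, and nothing in the plan adds the rest before Phase 3 starts. An SAE with onset after Day 43, or an imbalance between arms that appears only then, could be missing from the one by-arm tabulation tied to the go/no-go decision. That would be a reasonable price if waiting delayed the trial. The plan's own pause, however, is long enough for every Phase 2 subject to complete the Day 91 contact.

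**Working it through.** **1. The plan's own SAE figure.** Protocol 12.2 gives more than a 90% chance of at least one vaccine-related SAE among 1,100 vaccinees at a true rate of 0.21%. Check: 1 − (1 − 0.0021)^1100 = 0.901. It reproduces.

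**2. How much of the window is outside the cut.** Days 44-91 are 48 days, and 48/91 = 53%. After dose 2, the report covers 21 of 69 days (30%). The omitted time is 200 × 48/365.25 = 26 person-years in vaccinees, or 300 × 48/365.25 = 39 in all subjects.

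**3. Where subjects stand at the trigger.** Let calendar day 1 be the first injection and E the calendar day of the last subject's first injection. At the last Day 43 visit the first subject is on study day E + 42. Late visits add up to 8 days (+4 for Injection 2 in protocol 4.6.3, +4 for Day 43). The earliest permitted Day 91 contact is Day 81 (91 − 10).

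| Enrolment | E | First subject, nominal | With both windows late |
|---|---|---|---|
| 2 weeks (protocol summary) | 14 | Day 56 | Day 64 |
| 4 weeks (protocol summary) | 28 | Day 70 | Day 78 |
| 1.5 months (protocol 4.4, recruitment and screening) | 45 | Day 87 | Day 95 |

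Under 2-4 weeks, nobody has reached Day 81. If injections were spread over 1.5 months, some early enrollees could already have been called.

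**4. Whether Day 91 fits in the pause (E = 28; 1 month = 30.44 days).**
- Last Day 91 call: 28 + 90 = day 118, or day 128 at the +10 edge.
- Last second injection: 28 + 21 = day 49. A 6-month pause from there ends at 49 + 183 = day 232.
- Margin from last call to end of pause: 232 − 128 = 104 days.
- Lock at +56 days: day 174 to 184, leaving 48 to 58 days of a 6-month pause. An 8-10 month pause leaves more.

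**5. What the extra follow-up could show.** Assume a constant hazard, 100 subjects per arm and a 91-day risk p. The chance of at least one case in an arm is 1 − (1 − p × 43/91)^100 at the Day 43 cut, and 1 − (1 − p)^100 at Day 91.

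| p | Through Day 43 | Through Day 91 |
|---|---|---|
| 0.21% (protocol planning rate) | 9% | 19% |
| 1% (assumed) | 38% | 63% |
| 2% (assumed) | 61% | 87% |
| 3% (assumed) | 76% | 95% |

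With no SAE in 100 subjects, the exact two-sided 95% upper bound is 1 − 0.025^(1/100) = 3.6%, whichever cut is used.

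**The case against.** The Day 43 evaluation is a deliberate and disclosed choice, and late SAEs are not invisible. Protocol 9.3.1 requires SAE reports within 24 or 48 hours of site awareness. Section 4.6.4 has a safety team looking at events about weekly. Section 9.5.2 gives the DSMB unblinded cumulative data periodically, and Ministry of Health concurrence is also required. Phase 1 had no SAEs in 75 subjects, and SAE detection is planned on 1,100 vaccinees, not on 100 per arm. If vaccine-related risk clusters soon after dosing, the cut loses less than 53% of the information.

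Much of this stands, and it rules out several stronger readings:

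- *The DSMB may see Day 43 data only.* The Preface words Day 43 as a minimum, and 9.5.2 names no cut. The DSMB could see more; nothing requires it to.
- *The Phase 3 decision is made on less than half of the SAE period.* That is true of the planned tabulation. When the DSMB meets, most or all subjects may have passed Day 91, and known SAEs will have been reported.
- *The early cut saves no time.* The documents do not show this. Assays, unblinded programming, DSMB review and Ministry review all share the pause, and a 6-month pause leaves only 48 to 58 days after lock.
- *No subject can have reached Day 91.* This depends on 2-4 week enrolment.

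The safeguards still leave a gap. Expedited reporting starts when the site becomes aware, and the Day 91 call is the only scheduled SAE collection after Day 43. Investigators and others conducting the trial stay blinded, so weekly review gives no planned comparison between arms. Periodic DSMB review has no date tied to the start of Phase 3. The final SAP does not clearly close the gap later: its section VIII combines Phase 2 safety data only if needed, and only for the selected dose and placebo.

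**Conclusion.** The point holds as a gap in the content of the interim report, and only for SAEs. The planned by-arm tabulation omits 48 of 91 days of a pre-specified endpoint, and no provision requires the rest to be reviewed by arm before Phase 3. The missing follow-up will exist in time: under 4-week enrolment the last call is about calendar day 128, roughly 100 days before the shortest stated pause ends.

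The size is modest. With 100 subjects per arm, a rare event will probably be missed at either cut (9% versus 19% at 0.21%). The larger contrasts, such as 76% versus 95%, rest on assumed risks of 1-3%, and every row rests on a constant hazard. The timing rests on 2-4 week enrolment and on a 6-month pause counted from the last second injection. It uses the protocol as supplied, whereas the interim SAP cites protocol version 1.0. This is a cheap improvement, not a flaw that invalidates the Phase 3 decision.

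**What to change.** 1. Keep the Day 43 cut for HAI and MN results, reactogenicity and the preliminary dose recommendation.
2. In interim SAP section VIII, title the SAE table *SAEs through Day 43 (partial)*, so that it is not read as the Days 1-91 endpoint.
3. In the interim SAP Preface and section IX, and in protocol 9.5.2 and 28.2, add: *Before Phase 3 vaccination begins, the DSMB also receives a supplementary cumulative SAE table by treatment group (all three arms) through the Day 91 contacts of all Phase 2 subjects.* Full database lock is not needed for this table.
4. Reconcile the statements on listings. Interim SAP section VIII says that SAEs and other adverse events are listed, and section IX promises listings by group. Section VI.B and protocol 28.2 rule out individual listings.
5. Reconcile the 6-month and 8-10 month pause lengths, since the timing depends on them.

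The final SAP already describes Phase 2 as done and the dose as chosen. If the gate has been passed, the same three-arm table through Day 91 can still be specified in final SAP section VIII.

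Cost: one extra table and a few sentences, with no new visits or subjects. The DSMB's final advice would come after the last Day 91 call, still within the planned pause.
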